5.1.2.4 Neutrophil-lymphocyte Ratio (NLR) and Platelet-lymphocyte Ratio (PLR)

NLR will be derived using the ANC and absolute lymphocyte count (ALC), and PLR will be calculated using platelet count and ALC. Both NLR and PLR may have prognostic value in patients with various solid tumors. That is, the lower the value, the better the clinical prognosis. If data permit, NLR and PLR will be correlated with various anti-tumor efficacy analyses [e.g. objective response rate (ORR), PFS, and etc.].

5.1.3. Chemotherapy Exposure And Compliance Endpoints**5.1.3.1 Duration of Exposure**

Duration of exposure (days) = First dose date of study drug from the last cycle – first dose date of study drug + 21.

5.1.3.2 Number of Cycles Received

Patients are considered to have started a cycle if they have received at least one dose of any study drug (etoposide, carboplatin, and trilaciclib). In addition to the numeric summary for the number of cycles, the number of cycles will be categorized as 1, 2, 3, 4, 5, and ≥ 6 .

5.1.3.3 Dose Intensity and Cumulative Dose

Algorithms for calculating parameters relevant to the dose exposure and intensity are included in [Table 9](#).

Table 9 Algorithms for Calculating Parameters Relevant to the Dose Exposure and Intensity

Parameter	Trilaciclib [§]	Etoposide	Carboplatin
Dosing schedule per protocol	200 mg/m ² IV on Days 1 to 3 of a 3-week cycle	100 mg/m ² IV on Days 1 to 3 of a 3-week cycle	5 AUC on Day 1 of a 3-week cycle
Dose by cycle	Total dose administered (mg) / most recent BSA (m ²) [(mg/m ²)].	Total dose administered (mg) / most recent BSA (m ²) [(mg/m ²)].	Total dose administered (Prescribed AUC and actual dose in mg)
Cumulative dose	Sum of the doses administered to a patient in the duration of exposure [(mg/m ²)]	Sum of the doses administered to a patient in the duration of exposure [(mg/m ²)]	Sum of the doses administered to a patient in the duration of exposure (in total prescribed AUC and total dose in mg)
Dose intensity	Cumulative dose (mg/m ²) / (duration of exposure / 7) [(mg/m ² /week)]	Cumulative Dose (mg/m ²) / (duration of exposure / 7) [(mg/m ² /week)]	Cumulative Dose (total prescribed AUC) / (duration of exposure / 7) [AUC/ week]
Relative dose intensity (%)	100 * [Dose intensity (mg/m ² /week) / (600 / 3 (mg/m ² /week))]	100 * [Dose intensity (mg/m ² /week) / (300 / 3 (mg/m ² /week))]	100 * [Dose intensity (AUC/week) / (5/3 (AUC/week))]

Parameter	Trilaciclib [§]	Etoposide	Carboplatin
Relative Dose (%)	100 * [Cumulative dose (mg/m ²) / (600 × number of cycles (mg/m ²)]	100 * [Cumulative dose (mg/m ²) / (300 × number of cycles (mg/m ²)]	100 * [Cumulative dose (AUC) / (5 × number of cycles (AUC))]

[§] Two different doses (200mg/m² and 240mg/m²) of trilaciclib were evaluated in Part 1. 240mg/m² trilaciclib was the planned dose for all patients in Part 2. The calculation of relevant parameters will be adjusted accordingly based on the example presented in this table. AUC = area under curve; BSA = body surface area; IV = intravenous.

5.1.3.4 Modifications of Study Therapy, Including Cycle (Dose) Delay, Missed Doses, Dose Interruptions, and Dose Reductions

- After Cycle 1, patients need to meet pre-specified laboratory parameter criteria before initiating Cycle 2 and each subsequent cycle of chemotherapy. Cycle (dose) delay and its associated reasons are collected at the beginning of each cycle in an electronic case report form (eCRF) page titled “Beginning Cycle Assessment”. The reasons for delay will be summarized in the following categories: (1) Adverse event, (2) Logistical/Administrative Issues, (3) Hematologic Toxicity (which is a sum of those patients who fall into either category 3a or 3b), (3a) ANC < 1.5 x 10⁹/L, (3b) Platelet Count < 100 x 10⁹/L, (5) Nonhematologic Toxicity and (6) Other. Note that categories 3a and 3b are sub-bullets of category (3).
- Missed doses are identified on the dosing page. The reasons for missed doses will be summarized in the following categories: (1) Adverse Event, (2) Logistical/Administrative Issues, and (3) Other.
- Dose (mg/m²) reductions are not permitted for trilaciclib. Dose reductions for carboplatin and etoposide are collected on the dosing page; the reasons for reduction will be summarized in the following categories: (1) Adverse Event, (2) Change recommendation by SMC, and (3) Other.
- Dose interruptions for all drugs are also captured on the dosing page and will be summarized for each study drug.

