##### 8.4.3.1. Carboplatin

The carboplatin dose will be calculated using the Calvert formula with a target AUC = 5 on Day 1 of each 21-day cycle and administered as an IV infusion over 30 minutes. The Calvert formula is as follows:

$$\text{Total carboplatin dose (mg)} = (\text{target AUC}) \times (\text{GFR} + 25)$$

Because each patient's estimated GFR will be based on serum creatinine measurements obtained using standardized isotope dilution mass spectrometry, the **dose of carboplatin should be capped at 750 mg** to avoid potential toxicity due to overdosing. The cap dose of 750 mg for carboplatin is based on a GFR estimate that is capped at 150 mL/min for patients with normal renal function (ie, maximum carboplatin dose = target AUC of 5 mg•min/mL × 150 mL/min = 750 mg).

Refer to the carboplatin prescribing information (see [Appendix 2](#)) for details regarding preparation, administration, instructions and precautions. Premedications may be provided per local standard of care.

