### **8.9. Treatment Compliance**

The investigator or designee will dispense the study medication, via an unblinded pharmacist/designee, only for use by patients enrolled in the study as described in this protocol. The study drug is not to be used for reasons other than those described in this protocol. The investigator or other study staff will supervise each dose of the study drug administered in the clinic. The clinical study site will maintain records of study drug receipt, preparation, and dispensing, including the applicable lot numbers; patient's height, body weight, and BSA; date and time of the start and end of each G1T28 or placebo, etoposide, and carboplatin infusion; and total drug administered in milligrams. Any discrepancy between the calculated dose and dose administered and the reason for the discrepancy will be recorded on the electronic case report form (eCRF) and in the source documents.

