6.2.7.3. Exposure Endpoints

The extent of drug exposure and dose modifications is considered as important efficacy endpoints for trilaciclib. The study dosing records and the derived dosing endpoints will be listed.

Duration on treatment and number of cycles will be summarized by treatment. For each study drug, the dosing endpoints described in [Section 5.1.3](#) will be summarized by treatment.

Dose modification will be summarized for each study drug (trilaciclib, etoposide and carboplatin) including the following:

- Number of cycles received;
- Number of missed doses;
- Number of dose reductions;
- Number of dose interruptions;
- Number of patients with missed dose and its reason;
- Number of patients with dose reductions and its reason;
- Number of patients with dose interruption and its reason.

The number of cycles delayed, the number and percentage of patients experiencing a treatment cycle delay and reason for cycle delay will be summarized by treatment. The number of patients discontinuing study drug will also be summarized along with the reason for discontinuation.

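### SAP Table 9 builds carboplatin dose intensity, relative dose intensity and relative dose on prescribed AUC, so a part-delivered infusion does not lower them

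*SAP*

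**What the plan says.** SAP Section 5.1.3.3, Table 9, treats the three drugs differently.

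- **Etoposide and trilaciclib.** Dose by cycle is milligrams given divided by the latest body surface area. Cumulative dose, dose intensity and both relative measures follow from that.
- **Carboplatin, dose by cycle:** "Total dose administered (Prescribed AUC and actual dose in mg".
- **Carboplatin, cumulative dose:** described as a sum of what was administered, but expressed "in total prescribed AUC and total dose in mg".
- **Carboplatin, dose intensity:** "Cumulative Dose (total prescribed AUC) / (duration of exposure / 7", that is, per week of exposure.
- **Carboplatin, relative dose intensity:** "100 * [Dose intensity (AUC/week) / (5/3 (AUC/week".
- **Carboplatin, relative dose:** "100 * [Cumulative dose (AUC) / (5 × number of cycles (AUC". The only cumulative AUC that the table defines is the prescribed one.

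SAP Section 6.2.7.3 gives these summaries weight: "The extent of drug exposure and dose modifications is considered as important efficacy endpoints for trilaciclib". SAP Section 5.1.3.4 separately summarizes cycle delays, missed doses, reductions and interruptions.

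Protocol Section 8.4.3.1 doses carboplatin by the Calvert formula at target AUC 5, and the "dose of carboplatin should be capped at 750 mg". Protocol Section 8.4.4.2.1 foresees infusions being stopped for hypersensitivity. Protocol Section 8.9 has sites keep the total milligrams administered and adds: "Any discrepancy between the calculated dose and dose administered and the reason for the discrepancy will be recorded".

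**The concern.** The carboplatin cells describe administered doses but feed a prescription into the intensity and relative measures. The prescribed AUC changes when the dose level is reduced and, as written, does not change when the bag is not finished. A partial infusion then leaves dose intensity, relative dose intensity and relative dose where they were. The same shortfall in etoposide lowers all of that drug's measures, so two columns of one table, reported side by side as intensity of the same regimen, do not measure the same thing.

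The stake is how far the exposure tables can support a statement that chemotherapy intensity was maintained. Protocol Section 11.7 names maintained dose intensity as one way in which G1T28 might improve chemotherapy activity, and Protocol Section 13.4.1 lists dose intensity and cumulative dose as endpoints. A reader of the study report would take 100% relative carboplatin dose to mean that the planned amount was given.

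**Working it through.** **Inputs**

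- Prescribed AUC 5 per cycle; Table 9 references of 5/3 AUC per week and 5 × number of cycles.
- Duration of exposure (SAP Section 5.1.3.1): first dose date of the last cycle minus first dose date, plus 21. Six on-time cycles: 5 × 21 + 21 = 126 days = 18 weeks. Four: 3 × 21 + 21 = 84 days = 12 weeks.
- Assumption: the prescribed AUC is credited in full for a cycle with a partial infusion. Table 9 does not say otherwise.

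**Step 1. Table 9 with full delivery, six cycles.** Cumulative AUC 6 × 5 = 30. Dose intensity 30/18 = 1.667 AUC/week. Relative dose intensity 1.667/(5/3) = 100%. Relative dose 30/30 = 100%. The formulas behave as intended.

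**Step 2. One infusion partly delivered.** Under the assumption, Table 9 still returns 100% on both relative measures. Counting what was delivered:

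| Case | Delivered AUC | AUC/week | Both relative measures | Table 9 |
|---|---|---|---|---|
| 1 of 6 cycles, 75% given | 28.75 | 1.597 | 95.8% | 100% |
| 1 of 6 cycles, 50% given | 27.5 | 1.528 | 91.7% | 100% |
| 1 of 6 cycles, 25% given | 26.25 | 1.458 | 87.5% | 100% |
| 1 of 4 cycles, 50% given | 17.5 | 1.458 | 87.5% | 100% |

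A wholly omitted dose in one of six cycles would give 25/30 = 83.3% if scored as 0. Table 9 does not state this rule, although its reference to administered doses suggests it.

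**Step 3. The same event for etoposide.** The Table 9 reference is 300 mg/m² per cycle, so 1800 over six cycles. A shortfall of 50 mg/m² in one cycle gives 1750/1800 = 97.2%. The etoposide measure registers it.

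**Step 4. What the carboplatin measures do register.**

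- Dose reductions: AUC 5, 5, 4, 4, 4, 4 sums to 26, and 26/30 = 86.7%.
- Delay: 14 days in total gives 30/20 = 1.5 AUC/week, relative dose intensity 90.0%; relative dose stays at 100%.

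**Step 5. The milligram rows.** At an assumed GFR of 100 mL/min the planned dose is 5 × (100 + 25) = 625 mg, or 3750 mg over six cycles. One half-delivered infusion gives 5 × 625 + 312.5 = 3437.5 mg. The total falls, but Table 9 sets no planned milligrams against it.

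**Step 6. The cap.** Protocol Section 8.4.3.1 derives 750 mg as 5 × 150, and that product is correct. The Calvert formula in the same section adds 25 to GFR: a GFR of 150 gives 5 × 175 = 875 mg, while 750 mg at AUC 5 corresponds to 750/5 − 25 = 125 mL/min. The stated GFR limit and the formula do not lead to the same maximum.

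**The case against.** The strongest case on the other side is that little turns on this.

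- **Delivery is visible elsewhere.** Table 9 reports actual milligrams by cycle and in total, and SAP Section 5.1.3.4 counts interruptions and missed doses. A reader might infer from the prescribed-AUC formulas that a shortfall never reaches any reported exposure figure. The documents do not support that. What stands is narrower: the milligram rows have no denominator and the counts do not show how much was lost, so neither repairs the relative measures.
- **The cap.** A reader might infer that a capped patient scored at 100% is also overstated, for example at 750/175 = 4.29 AUC, or 85.7%, for an assumed GFR of 150. The documents do not support that either. The cap is part of the regimen (Protocol Synopsis, Sections 8.1 and 8.4.3.1), so 750 mg fully infused is the full protocol dose. The 85.7% also depends on a GFR that Section 8.4.3.1 leaves unsettled for capped patients; at 125 the result is 100%. This objection stands in full.
- **Size.** A half-delivered infusion could be described as a 50-point overstatement, but Table 9 has no per-cycle relative measure. Over six on-time cycles the difference is 100 − 91.7 = 8.3 points.
- **Relevance.** The hypothesized benefit is fewer delays and blood-count-driven reductions, which prescribed AUC and calendar time capture. Exposure is not among the prospectively defined analyses in SAP Table 3, and SAP Section 6.2.7 restricts between-arm comparison to the Section 5.1.1 endpoints. This limits the consequence, but it does not make the formula measure delivery.

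**Conclusion.** The point holds for stopped or partial infusions. As written, three carboplatin exposure measures cannot fall when an infusion is not completed, unlike the matching measures for etoposide and trilaciclib. For a patient with one half-delivered infusion the overstatement is 8.3 points over six on-time cycles and 12.5 points over four (100 − 87.5). Both figures assume that the prescribed AUC is entered unchanged for the affected cycle.

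The documents do not say how many patients would be affected, so no effect on arm-level summaries can be stated. A reader might infer a bias between arms; nothing in the documents shows that partial infusions would be unbalanced, and no test uses these measures. This is a correction worth making to a descriptive endpoint that the SAP calls important. It does not threaten the trial's main conclusions.

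Separately, the GFR limit and the Calvert formula in Protocol Section 8.4.3.1 give different maximum doses at AUC 5 (875 mg against 750 mg) and must be reconciled. This review takes no view on which is right.

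**What to change.** In SAP Table 9, define for each cycle:

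*delivered carboplatin AUC = prescribed AUC × (mg administered / protocol-calculated mg for that cycle, after the 750 mg cap)*

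Count an omitted carboplatin dose as 0. Use this quantity for cumulative AUC, dose intensity, relative dose intensity (reference 5/3 per week) and relative dose (reference 5 × number of cycles). Keep prescribed AUC and total milligrams as descriptive rows.

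Check in the Step 5 example: 5 × 312.5/625 = 2.5 for the affected cycle, so the six-cycle total is 27.5 and the relative dose 91.7%. A capped dose given in full scores 5 × 750/750 = 5, or 100%.

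Dividing milligrams by GFR + 25 instead would be less sound. No section lists the GFR used for dosing as a recorded item, and its value for capped patients is unclear.

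**Cost.** A small table edit and slightly lower reported intensity. No new data should be needed, since the SAP already requires actual milligrams and the protocol records discrepancies from the calculated dose. Before adopting it, confirm that the eCRF entry yields the calculated milligrams and that they are taken after the cap.

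**Limit.** Reductions in capped patients are still scored on the AUC scale. At an assumed GFR of 150, moving from AUC 5 to AUC 4 takes the dose from 750 mg to 4 × 175 = 700 mg, a fall of 50/750 = 6.7%, while AUC falls by 20%. The milligram row should stay for that reason.

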5.2. Safety Endpoints

5.2.1. Adverse Events (AEs)

All AEs will be coded from verbatim text to PTs and grouped by SOC using the MedDRA Version 20.1. AEs will be collected from the time of signature of informed consent throughout the treatment period and including the post-treatment visit. AEs are graded by investigator according to CTCAE, Version 4.03.

Any AE that started on or after the first dose of study drugs and up to the last dose +30 days will be included as a treatment-emergent AE (TEAE). AEs with an unknown/not reported onset date will also be included.

Other AE variables include drug-related AEs, AEs leading to study drug discontinuation or study withdrawal, AEs leading to death, SAEs.

AEs with onset/end dates that are partially/completely missing will be imputed as follows:

(i) For onset date:

- If only the day part of the AE onset date is missing and occurs in the same month and year as the first dose date of study drug, the date of first dose of study drug will be used as the onset date of the AE. Otherwise, the first day of the month will be used to complete the onset date of the AE;
- If the day and month parts of the AE onset date are missing and occur in the same year as the first dose of study drug, the date of the first dose of study drug will be used as the onset date of the AE. Otherwise, January 1st will be used to complete the onset date of the AE;
- If the AE onset date is completely missing, the date of the first dose of study drug will be used as the onset date of the AE.

(ii) For end date:

- If only the day part of the AE end date is missing, the last day of the month will be used to complete the end date of the AE;
- If the day and month parts of the AE end date are missing, December 31st will be used to complete the end date of the AE;
- If the AE end date is completely missing and the onset date of the AE occurs after the date of the first dose of study drug, the last date during the treatment period +30 days will be used as the AE end date. If the AE end date is completely missing and the onset date of the AE occurs prior to the date of the first dose of study drug the date of the first dose of study drug will be used as the AE end date.

AEs related to hematologic toxicity will be pooled based on the preferred MedDRA Version 20.1. [Table 10](#) outlines those terms that will be consolidated.

Table 10 Preferred Terms to Be Consolidated

Presented term in the table	Preferred Term
Neutropenia	Neutropenia
	Febrile neutropenia
	Neutrophil count decreased
Anaemia	Anaemia
	Anaemia macrocytic
	Red blood cell count decreased
	Hemoglobin decreased
Thrombocytopenia	Thrombocytopenia
	Platelet count decreased
Lymphopenia	Lymphopenia
	Lymphocyte count decreased
Leukopenia	Leukopenia
	White blood cell count decreased

AEs potentially related to infusion reactions will be pooled based on the PTs of MedDRA Version 20.1. The events described by the PTs listed below that have a start date on the same

date study drug is administered will be summarized and presented in order of decreasing frequency: angioedema, back pain, bronchospasm, wheezing, chest pain, non-cardiac chest pain, hyperhidrosis, malignant dysphagia, dysphagia, oedema, swelling face, flushing, dysphonia, hypotension, hypoxia, paraesthesia oral, pain, phlebitis, pruritic, pyrexia, rash, dermatitis allergic, drug eruption, infusion site rash, injection site rash, rash pruritic, erythema, infusion site erythema, injection site erythema, chills, dyspnoea, syncope, tachycardia, throat tightness, injection site ulcer and mucocutaneous ulceration.

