- c Monthly phone calls will be made to each patient that is in the long-term Survival Follow-up Phase. Patients will be followed for survival until at least 50% of the patients in Part 2 have died. Any anticancer therapies used will be collected. In addition, blood samples for hematology and immunologic marker assessment will be collected at  $60 \pm 7$  days after the Post-Treatment Visit for patients in Part 2 only.
- d Informed consent may be obtained up to 28 days prior to the first study treatment administration.
- e Including medical, surgical, radiation history, smoking history, family history, documentation of tumor diagnosis, baseline signs and symptoms within 4 weeks prior to randomization, weight loss in the 6 months prior to randomization ( $\leq 5\%$  or  $> 5\%$ ), and medications taken within 14 days of enrollment.
- f Height will only be measured at the screening visit. Body surface area calculation (based on actual body weight) will be completed on Day 1 of each cycle and vital signs obtained immediately before and after G1T28 or placebo and E/P infusions. Vitals only need to be taken once between infusions.
- g Clinical chemistry will be obtained (albumin, alkaline phosphatase, total bilirubin, calcium, chloride, creatinine, glucose, inorganic phosphorus, potassium, total protein, ALT, AST, lactate dehydrogenase [LDH], sodium, and blood urea nitrogen [BUN]); see Section 11.3.2. Clinical chemistry and urine analysis may be obtained up to 72 hours prior to the first dose of each cycle of G1T28 or placebo + E/P therapy.
- h Hematology will be obtained (hemoglobin, hematocrit, WBCs with differential, and platelet counts); see Section 11.3.2. Hematology may be obtained up to 24 hours prior to first dose of each cycle of G1T28/placebo + EP therapy.
- i In Part 2 only, hematology will be collected at 60 days after the Post-Treatment Visit.
- j Patients participating in the Phase 1b dose-finding portion of Part 1 of the study, who have PK samples obtained, will have ECGs completed at the following time points on Days 1 and 3 of Cycle 1: predose, end of infusion (EOI) of G1T28, 2 hours ( $\pm 10$  minutes) after the start of G1T28, and 6.5 hours ( $\pm 15$  minutes) after the start of G1T28. The 2-hour ECG will be completed once the etoposide infusion is complete.

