### 10.1. Screening

Patients should be screened no more than 14 days before the first dose of study treatment is administered. Written informed consent must be obtained from each patient before the initiation of any screening procedures. Informed consent and brain scans may be obtained up to 28 days prior to the first study treatment administration. After a patient has given informed consent, eligibility will be determined by a review of the inclusion/exclusion criteria and completion of all screening procedures outlined in Table 9-1 and listed below.

- Collection of demographics
- Collection of medical history
- ECOG performance status evaluation
- Physical examination
- Height, weight, and vital signs measurements
- Clinical chemistry, hematology, and urinalysis tests
- Electrocardiogram
- Pregnancy test
- Tumor assessment (by CT scan or MRI; see details in Section 11.5.1); CT or MRI scans obtained prior to informed consent will not need to be repeated if performed within 14 days prior to dosing.
- Brain scan with contrast (by MRI or CT); brain MRI or CT scans obtained prior to informed consent will not need to be repeated if performed within 28 days prior to dosing.

Adverse events and concomitant medications will be monitored continuously from the time of informed consent through the Post-Treatment Visit.

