6.2.5. Concomitant Medications

All medication verbatim terms collected will be coded to Anatomical Therapeutic Classification (ATC) and PT using the WHO-DD Version Sep2017.

Prior medications are defined as those taken by the patient prior to the administration of study drug. Concomitant medications are defined as those taken by the patient at any time between the date of study drug administration and study completion/discontinuation. Medication with start date/time being partially or completely missing will be assumed to be concomitant if it cannot be definitely shown that the medication did not occur during the treatment period.

Medications with onset/end dates that are partially/completely missing will be imputed as follows:

(i) For onset date:

- If only the day part of the medication onset date is missing and occurs in the same month and year as the first dose date of study drug, the date of first dose of study drug will be used as the onset date of the medication. Otherwise, the first day of the month will be used to complete the onset date of the medication;
- If the day and month parts of medication onset date are missing and occur in the same year as the first dose of study drug, the date of the first dose of study drug will be used as the onset date of the medication. Otherwise, January 1st will be used to complete the onset date of the medication;
- If the medication onset date is completely missing, the date of the first dose of study drug will be used as the onset date of the medication.

(ii) For end date:

- If only the day part of the medication end date is missing, the last day of month will be used to complete the end date of the medication;
- If the day and month parts of medication end date are missing, December 31st will be used to complete the onset date of the medication;
- If the medication end date is completely missing and the onset date of the medication occurs after the date of the first dose of study drug, the last date during the treatment period will be used as the medication end date. Otherwise, the date of the first dose of study drug will be used as the medication end date.

Concomitant medications will be summarized by presenting the number and percentage of patients by PT and ATC. Patients taking the same medication multiple times will only be

counted once for that PT or ATC. Each summary will be ordered by descending order of incidence of ATC class and PT within each ATC class.

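### SAP 5.2.1 can set an incomplete AE onset to the first-dose date even when the recorded end date is earlier, so an event that was over before dosing becomes treatment-emergent

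*SAP*

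**What the plan says.** **Collection starts before dosing.** SAP 5.2.1: "AEs will be collected from the time of signature of informed consent throughout the treatment period". Protocol Table 9-1: "Informed consent may be obtained up to 28 days prior to the first study treatment administration". Events that begin and end before any study drug are therefore in the database.

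**Treatment emergence is decided on onset.** SAP 5.2.1 counts "Any AE that started on or after the first dose of study drugs and up to the last dose +30 days" and adds: "AEs with an unknown/not reported onset date will also be included". Neither statement mentions the end date.

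**Three onset patterns go to the first-dose date:**
- completely missing: "If the AE onset date is completely missing, the date of the first dose of study drug will be used as the onset date";
- day missing: "If only the day part of the AE onset date is missing and occurs in the same month and year as the first dose" date;
- day and month missing, with the year matching that of first dose.

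Other partial onsets go to the first of the known month or to 1 January of the known year.

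**The imputed dates are used.** SAP 6.1.2 states that they determine the status of each AE.

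**End dates.** When the end date is completely missing, 5.2.1(ii) gives one rule for onsets after first dose and one for onsets before it. An onset on the first-dose date is not mentioned.

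**Medications.** SAP 6.2.5 has a status guard. A medication with an incomplete start "will be assumed to be concomitant if it cannot be definitely shown that the medication did not occur during the treatment period".

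**The concern.** Assuming that an AE is on-treatment when its timing is unknown is a sensible conservative choice. It is not conservative when the record already shows that the event was over before dosing. In that case the rule overrides known data and creates an impossible interval, with onset after end.

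Protocol 13.5.2 defines a treatment-emergent AE as one occurring from the day of first dose onward, which such an event cannot satisfy. SAP section 7, which lists departures from the protocol's statistics section, does not mention a change to this definition.

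Safety and tolerability is the primary objective that applies to Part 2, and these tables report it. There are two further effects:
- An onset placed on Day 1 also meets the same-day timing condition for potential infusion reactions in 5.2.1. The listed terms include dyspnoea, chest pain and back pain.
- The cycle-overlap rules for febrile neutropenia and infection SAEs (SAP 5.1.1.1 and 5.1.1.7) refer back to 5.2.1 for missing dates. They give no defined result for an interval whose start follows its stop.

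**Working it through.** The plan gives no figure to reproduce here. The check applies the 5.2.1 rules literally.

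**Step 1: test cases.** The dates are assumed for illustration: first dose 15 June 2017, last dose 1 October 2017, recorded AE end 10 June 2017.

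| Recorded onset | Imputed onset | Treatment-emergent? | Onset after end? |
|---|---|---|---|
| completely missing | 15 June 2017 | yes | yes, by 5 days |
| June 2017 | 15 June 2017 | yes | yes, by 5 days |
| 2017 | 15 June 2017 | yes | yes, by 5 days |
| May 2017 | 1 May 2017 | no | no |
| 2016 | 1 January 2016 | no | no |

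The first three rows fail. The last two do not, so the error is confined to the three patterns that default to first dose.

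**Step 2: how far each pattern reaches.** Take every AE that starts and ends within the 28 days before first dose, for each first-dose day of a 365-day year. With start s days before dosing (1 to 28) and end between s days and 1 day before, there are 28 × 29 / 2 = 406 start/end pairs. Over the year this gives 406 × 365 = 148,190 combinations.

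- *Onset completely missing:* all fail. 148,190 / 148,190 = 100%.
- *Only the year known:* a combination escapes only if the event began in the previous calendar year, which needs a first dose on 1 to 28 January. The number escaping is the sum of s² for s = 1 to 28, which is 28 × 29 × 57 / 6 = 7,714. Failing: 148,190 − 7,714 = 140,476, or 94.8%.
- *Only the day missing:* a combination fails if the start falls in the same calendar month as first dose. That gives 4,872 failing combinations for each 31-day month, 4,466 for each 30-day month and 3,654 for February. Total: 7 × 4,872 + 4 × 4,466 + 3,654 = 55,622, or 37.5%.

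These shares weight all combinations equally. They describe how the rule behaves once an AE is pre-dose with that kind of missing onset. They do not estimate how often such AEs occur.

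**Step 3: with a guard.** If first-dose imputation is allowed only when the end date is missing or on or after first dose, the three failing cases become not treatment-emergent and none keeps an onset after its end.

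**Step 4: the end-date gap.** An AE with onset and end both completely missing is given the first-dose date as onset. Rule (ii) then needs that onset to be after or before first dose. It is neither, so no end date is defined. The same applies to an AE that truly began on Day 1 and has no recorded end. The medication rules avoid this gap by sending every other case to a default.

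**The case against.** **Rarity and data cleaning.** The event must start after consent, end before dosing, and have a known end but an incomplete onset. Most screening is done within 14 days of dosing, and pre-existing conditions that do not worsen are not AEs (Protocol 11.3.1.1). Onset date is recorded for every AE (11.3.1.7), missing eCRF data must be accounted for (16.1), and discrepancy reports go to the investigator (section 14). SAP 6.2.8.1 lists all AEs, so an impossible interval would be visible. This stands as a reason to expect few cases. It does not repair the rule, which exists for dates that remain incomplete after cleaning.

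**No bias between arms.** Part 2 is randomized and double-blind, and events before dosing cannot depend on the study drug received. This also stands: the rule over-includes in both arms, and nothing shows that it favours one.

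**The medication contrast is only partial.** The medication onset rules match the AE rules and also lack an end-date check. What medications have, and AEs lack, is the guard on status.

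**Stronger readings that the documents do not support.** A reader might infer that the rule creates false Day 1 events in the composite of major adverse hematologic events (MAHE), each worth 1 of 35 patients in an arm.
- The febrile neutropenia component follows 5.1.1.1, which already uses the stop date. An inverted interval gives at most an undefined result.
- A hospitalization is an SAE, and onset is required on the SAE form (Protocol 11.3.1.11). Some of the hospitalization terms also receive medical review (SAP Table 6).
- Prior chemotherapy for SCLC and serious active infection are exclusions, and entry needs ANC of at least 1.5 × 10⁹/L. A febrile neutropenia that resolves before dosing is remote.
- MAHE is analysed as time to first event, so a difference in percentage points is the wrong scale.

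A reader might also infer that every partial onset goes to first dose. Step 1 shows that this is not so.

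**Conclusion.** The rule is wrong as written, but the point is minor. For an AE with a recorded end before first dose, a completely missing onset always yields a treatment-emergent event with onset after end. A partial onset does so only when its known month and year, or its year alone, match first dose. The undefined end date for a Day 1 onset is a second, separate gap.

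The size cannot be derived. The documents give no AE count, no rate of incomplete onsets and no share of AEs that end before dosing, so any figure for false treatment-emergent events would rest wholly on assumption. The number is probably small. The conclusion needs only the text of 5.2.1 and 6.1.2, the collection window and the protocol's definition.

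**What to change.** In SAP 5.2.1:

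1. **Onset rules (i).** Impute to the first-dose date only if the AE end date is missing or could be on or after first dose. If the known or partly known end date is definitely before first dose, classify the AE as pre-treatment. Never impute an onset later than the end date.
2. **Sentence on unknown onsets.** Add: *unless the end date is before the first dose*. Without this, the sentence would still make such AEs treatment-emergent and would conflict with the revised rule (i).
3. **End-date rules (ii).** Change *after* to *on or after* the first-dose date, so that Day 1 onsets are covered.

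The cost is a few words of text and one programming condition. No endpoint, analysis set or design element changes. AEs whose timing is truly unknown stay treatment-emergent, so the conservative intent is kept.
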